12.7.6 Ordinal Scale for Clinical Improvement (OSCI) at 7, 14 and 28 days

WHO Ordinal Scale for Clinical Improvement will be evaluated at baseline, 7, 14 and 28 days, as described in Section 8.6.

To investigate the effects of hMSCs treatment on clinical outcome as measured by the OSCI, a longitudinal mixed-effects proportional odds ratio model will be estimated and tested. Prior to final modeling, descriptive statistics of the response categories will be tallied. The assumption of proportionality will be tested and, if not met, a model relaxing that assumption will be used. (22)

Additionally, OSCI will be aggregate stratified by COVID-19 status and perform the modeling specified above by adjusting for COVID-status.

12.7.7 Glasgow Outcome Score at Hospital Discharge

Neurocognitive function measured by the Glasgow Outcome Score at hospital discharge will be recorded. If there are multiple scores on the date of hospital discharge, the score closest to the time of hospital discharge will be used. If the score is missing on the date of hospital, we will impute the score using the following methods:

- If patient is discharged to home, the score is assigned as 15;
- If patient is expired prior to hospital discharge, the score is assigned as 3;
- If patient is discharged to other facility, the score will not be imputed and left as a missing value.

Glasgow Outcome Score at hospital discharge will be summarized as mean with standard deviation, or median with inter-quartile range, and analyzed by appropriate bivariate analysis.

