	
days after enrollment).
 
Systemic illness endpoint: Sequential Organ Failure Assessment (SOFA) score at 3, and 7 days; in hospital mortality at 14, 28 and 60 days; additional prognostic value of neutrophil:lymphocyte ratio; ordinal scale for clinical improvement at 7, 14 and 28 days.
 
Neurocognitive endpoint: Neurocognitive function measured by the Glasgow Outcome Score at hospital discharge
 
Thromboembolic: Incidence of thromboembolic events measured by ultrasound of the deep venous system or CT-angiography of the chest ordered for clinical purposes/by treating clinicians; additional prognostic value of fibrinogen at baseline.
 
Biomarkers:
 
Plasma: Change in levels of plasma, urine and genetic biomarkers from baseline compared to 6, 24, 48, and 72 hours including: endothelial injury (angiopoietin-2), lung epithelial injury (Receptor for Advanced Glycation Endproducts [RAGE]), pro-inflammatory pathways (interleukin-6 [IL-6], interleukin-8 [IL-8], soluble tumor necrosis factor-1 [sTNF-1], intercellular adhesion molecule-1 [ICAM-1], interferon gamma-induced protein-10 [IP-10], interleukin-10 [IL-10], vascular endothelial growth factor [VEGF], matrix metalloproteinase-8 [MMP-8], thrombomodulin, surfactant protein-D [SP-D], triggering receptor expressed on myeloid cells-1 [TREM-1], interleukin-18 [IL-18], plasminogen activator inhibitor-1 [PAI-1]), impaired coagulation (protein C), pro-resolving lipids (lipoxin A4, Resolvin D₁), biomarkers that reflect the paracrine activity of the administered hMSCs (angiopoietin-1 [Ang-1] and keratinocyte growth factor [KGF]). Changes in levels of plasma SARS-CoV-2 viral antigen and antibody levels at multiple timepoints; gene expression at baseline and on day 2 and 3.
 
Alveolar fluid: Lung protein permeability as measured by total protein in mini-bronchoalveolar lavage [mBAL] protein at day 2; the same biomarkers will also be measured in plasma to compare hMSCs versus placebo treated patients.
 
Urine: Microalbumin will also be measured at 24 and 48 hours
 
Others: Primary and secondary endpoints will be adjusted by SARS-CoV2 infection to better understand the hMSC effects in patients with COVID-19 disease.

Name of Sponsor – Investigator	[name] University of California, San Francisco
Investigational Product	Allogeneic Bone Marrow-derived Human Mesenchymal Stromal Cells (hMSCs)

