- Superficial incisional/wound infections during the 14 days after enrollment.
- Deep incisional wound infections during the 14 days after enrollment.
- Organ (such as lung, liver) or space (such as peritoneum or pleural) infections during the 14 days after enrollment.
- Ventilator associated pneumonia (VAP) during the 14 days after enrollment.

3. Systemic Illness: Systemic illness efficacy endpoints will include:

- Mean SOFA score (127) at days 3, and 7.
- In hospital mortality at 14 days, 28 days, and 60 days.
- Additional prognostic value of neutrophil:lymphocyte ratio.
- Ordinal Scale for Clinical Improvement (OSCI) at days 7, 14 and 28.

To assess organ failure, we will measure serum creatinine (renal function), bilirubin (hepatic function), and platelet count (hematology) at days 0, 3, and 7.

4. Neurologic: Neurocognitive efficacy endpoints will include:

- Neurocognitive function at hospital discharge by the Glasgow Outcome Score (6 points)

5. Thromboembolic: Thromboembolic safety endpoints will include:

- Incidence of thromboembolic events: Measured by ultrasound of the deep venous system or CT-angiography of the chest when clinically indicated.
- Additional prognostic value of fibrinogen at baseline.

6. Biologic: Biomarker analysis will include: Changes in levels of plasma, urine, and genetic biomarkers at baseline compared to 6, 24, 48, and 72 hours, including:

- Endothelial injury (angiopoietin-2 [Ang-2])
- Lung epithelial injury (Receptor for Advanced Glycation Endproducts [RAGE])
- Pro-inflammatory markers (interleukin-6, interleukin-8, soluble tumor necrosis factor-1 [sTNF-1], intercellular adhesion molecule-1 [ICAM-1], interferon gamma-induced protein-10 [IP-10], interleukin-10 [IL-10], vascular endothelial growth factor [VEGF], matrix metalloproteinase-8 [MMP-8], thrombomodulin, surfactant protein-D [SP-D], triggering receptor expressed on myeloid cells-1 [TREM-1], interleukin-18 [IL-18], plasminogen activator inhibitor-1 [PAI-1])

- Protein C (marker of impaired coagulation)
- Pro-resolving lipids (lipoxin A4, resolvin D₁)
- Biomarkers that reflect the paracrine activity of the administered hMSCs (angiopoietin-1 [Ang-1], keratinocyte growth factor [KGF])

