9.11 Day 28 Measurements

Patients will be followed daily for adverse events through day 28 after study product administration, death or hospital discharge, whichever occurs first. If a patient is discharged from hospital before day 28, investigators will follow-up by phone interview with the patient, family member or caregiver after day 28 to ensure that no adverse events have occurred through day 28. Mechanical ventilation history (on or off ventilator support), ICU history and the need for dialysis through day 28 after study product administration will also be collected. Decisions about hospital discharge will not be made by study personnel; rather such decisions will be made by clinicians caring for the study subject based on the underlying condition that led to the hospitalization. Also, we will assess neurologic status by the 6 point Glasgow Outcome Score at hospital discharge.

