Appendix A: Time-Events Schedule

Measurement/Event	Prior to randomization	Day 0	During and after MSC infusion	1	2	3	4	5	6	7	8	9	10	11	12	13	14	28	60	6m
Demographics, History & Physical, Height, Weight	X																			
Etiology of ARDS	X																			
HCG (in females of childbearing age < 50 years old)	X																			
Baseline stability assessment (Vital signs and ventilator parameters) ^{S,B}		X																		
Mechanism of injury and trauma registry index (if applicable)	X																			
APACHE III Score ^C	X																			
ECHO ^D	A																			
COVID-19 test	A																			
COVID-19 vaccination status	A																			
Co-enrollment with other clinical trials and COVID-19 related therapies ^M	X			A	A	A	A	A	A	A	A	A	A	A	A	A	A	A		
Vital Signs (HR, SBP, DBP, MAP, Temp °C, SpO2) ~\$	X	X	X	X	X	X	X	X	X	X	X	X	X	X	X	X	X	X		
Central Venous Pressure ~\$	A	A	A	A	A	A	A	A	A	A	A	A	A	A	A	A	A	A		
Record vasoressors or inotropes * (Y/N)S	X	X	X	X	X	X	X	X	X	X	X	X	X	X	X	X	X	X		
Fluids in/out, crystalloids, PRBC, FFP, platelets, cryoprecipitate, urine output	X	X	X	X	X	X	X	X	X	X	X	X								
Modified Brussels Score and Brussels Organ Dysfunction Failure~E	X			X	X	X	X	X	X	X	X	X	X	X	X	X	X	X		
Sequential Organ Failure Score	X																		X	
Ventilator Parameters (including FiO2) #	X	X	X	X	X	X	X	X	X	X	X	X								
Arterial Blood Gases (PaO2, PaCO2, pH, SpO2, base deficit)&	X	X	X	X	X	X	X	A	A	A	A	X								
Chest X-ray (# quadrants for lung injury score, RALE score)	A			A	A	A	A	A	A	A	A	A	A	A	A					
Pulmonary dead space ^F	X							X	X	X										
Creatinine%G,H	X							A	A	X	A	A	A	X	A	A	A	A	A	
Total bilirubin, ALT, platelets%H	X							A	A	X	A	A	A	X	A	A	A	A	A	
D-dimer, lymphocyte count, neutrophil counts, fibrinogen, ferritin and serum C-reactive protein (if applicable)	A	A		A	A	A	A	A	A	A	A	A	A	A						
Glasgow coma score ^I	X	X						X	X	X									X	
Outpatient medication and on-study medication and study procedure ^K	X							X	X	X	X	X	X	X						
DVT Prophylaxis medication [¶]	X	X	X	X	X	X	X	X	X	X	X	X	X	X	X	X	X	X		
Positive blood culture [¶]	X							X	X	X	X	X	X	X	X	X	X	X		
Thromboembolic complications [¶]	X							X	X	X	X	X	X	X	X	X	X	X		
Wound site infection and VAP assessment ^E	X							X	X	X	X	X	X	X	X	X	X	X		
Blood for cytokines, mediators and markers of inflammation ^N		X	X	X																
Blood for DNA/RNA		X																		
Urine for biomarker measurements ^O		X																		
Mini-BAL																				

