Ventilator history and ICU history [@]																			X	
Need for, timing and duration of dialysis																		X	X	
Vital Status §																		X	X	
Ordinal Scale for Clinical Improvement (OSCI)	X														X			X	X	
Incidence of barotrauma		X						X	X	X				X						

X=Required; A=When available; ~Data gathered on days 0-14 or until d/c from study hospital; \$=Data recorded every 15 minutes for at least two hours during "stable baseline" period and until the initiation of study product infusion, every 15 minutes for the duration of the infusion and every hour until 6 hours, then 12, 24 and 48 hour from the initiation of study product infusion; #Data recorded every 15 minutes for at least two hours during "stable baseline" period and until the initiation of study product infusion, every 15 minutes for the duration of the infusion and every hour until 6 hours, then 12, 18, 24 and 36 hour from the initiation of study drug infusion, then day 2, 3, 4, 5, 6, and 7; &=ABG mandatory at the following timepoints: within 6 hours of randomization, prior to the start of the infusion (within 90 minutes of starting the baseline stability period); within 15 minutes of the end of MSC infusion (~1 hour); after the initiation of the study product infusion, ABGs will also be REQUIRED at 6, 12, 18, 24, 30, 36 hours (+/- 1 hour for all timepoints), day 2 (48 hours +/- 4 hours), 3 and 7 (anytime) if patient still has arterial line after study product infusion; €=Record only one episode during the 14 day period after study product infusion, no need for further assessment once first diagnosis is confirmed; %=Labs not available in the 24 hours before randomization must be obtained; ¶=Data gathered for first 14 days during current hospital admission; @=Measure at day 28. The 28-day follow up will be a telephone interview with structured survey if patient discharged prior to day 28; §=Measure at day 28, day 60, hospital discharge alive, and 6 months; the 6 month follow up will be a telephone interview with structured survey. B=Patient must achieve a stable baseline for ≥ 2 hours and the administration of study product must be initiated within 14 days of initial ICU admission; C=Record available clinical data within 24 hours prior to study randomization; D=Record ECHO if available. If more than one ECHO data available, select the data closest to randomization; E=Record clinically available worst SBP, PaO2/FiO2, SpO2/FiO2, creatinine, platelets, bilirubin, and vasoressor use; F=Measured on day 0, 1, 2, 3, 7 when patient is on assisted breathing; G=Record clinically available creatinine in the 96 hours prior to randomization, the worst creatinine of the day from day 1-14, the date and value of the highest creatinine between days 15-28 and the lowest value during the entire hospitalization obtained off dialysis; H=Data required prior to randomization, day 3 (+/-1 day) and day 7 (+/-1 day); J=Mandatory at the following timepoints: pre-randomization, pre-infusion, day 1, 2, 3, 7, 14 and the date of hospital discharge; K=Record outpatient medication (anticoagulants/antiplatelets/antifibrinolytic) within 7 days prior to current hospital admission; record the following medication and procedures (glucocorticoids, NMBD, inhaled vasodilators, prone positioning, recruitment maneuvers, ECMO) prior to randomization and on day 1-7; and inpatient trauma specific medications for first 14 days during current hospital admission; M= Record any co-enrollment of clinical trials and COVID-19 related therapies within 7 days prior to current hospitalization until hospital discharge; N=Blood specimens are required before the study product infusion, at 6, 12, 24 hours (+/- 1 hour), and 2 (48 hours +/- 4 hours), 3 days (anytime) after the initiation of the study product infusion. O=Urine specimens are required before the study product infusion, at 24 hours and 2 days (48 hours +/- 4 hours) after the initiation of the study product infusion.

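### SAP 12.7.7 fills in a missing 6-point Glasgow Outcome Score with 15 or 3, which no six-level whole-step scale can both hold, so the instrument analysed is unclear

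*SAP*

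**What the plan says.** The Protocol Synopsis gives the neurocognitive endpoint as "Neurocognitive function measured by the Glasgow Outcome Score at hospital discharge". Protocol 6.2.1 and SAP 7.2.1 both add that the score has 6 points, and Protocol 9.11 orders it: "we will assess neurologic status by the 6 point Glasgow Outcome Score at hospital discharge".

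SAP 12.7.7 keeps that name and sets rules for a score missing at discharge:

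- Home discharge: "If patient is discharged to home, the score is assigned as 15".
- Death: "If patient is expired prior to hospital discharge, the score is assigned as 3".
- Discharge to another facility: no imputation; the score stays missing.

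The same section covers repeated measurement: "If there are multiple scores on the date of hospital discharge, the score closest to the time of hospital discharge will be used". The score is then summarised as mean with SD or median with interquartile range, and compared between arms by a bivariate test.

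The schedules (Protocol Appendix A, SAP Table 2) have no Outcome Score row. The only Glasgow row in each is "Glasgow coma score". A footnote in each schedule reads "J=Mandatory at the following timepoints: pre-randomization, pre-infusion, day 1, 2, 3, 7, 14 and the date of hospital discharge".

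**The concern.** The imputed values belong to a different scale from the one the endpoint names. Either the 15/3 rule is wrong, or the endpoint's name and the 6-point description are wrong.

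Better neurocognitive function at discharge is a stated secondary objective in section 4.2 of both documents. As the plan stands, a reader of the results could not say which instrument produced them. If the 6-point score is analysed and the rule is applied as written, impossible values enter its mean and SD. On the usual kinds of coding, imputed deaths would also not count as the worst outcome.

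**Working it through.** There is no planned figure to reproduce. The check has three parts: a range check, a comparison of the sections, and the size of the effect if the 6-point score is the one analysed.

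**Range check.** Inputs: 6 levels (Protocol 6.2.1 and 9.11, SAP 7.2.1); imputed values 15 and 3 (SAP 12.7.7). The gap is 15 − 3 = 12, so a scale in whole steps that contains both needs at least 12 + 1 = 13 levels. No run of six consecutive integers contains both. A six-level coding with wider steps could (0, 3, 6, 9, 12, 15, for example), but no such coding is defined. Neither SAP section 8 nor the protocol appendices give the score's range, direction or death category.

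**Which instrument?**

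Pointing to the coma score:
- It is the only Glasgow row in either schedule.
- As the tables read, that row carries the marker I, no footnote I exists, and footnote J belongs to no row. J therefore appears to be its footnote, which would make the coma score mandatory on the day of discharge.
- The rule for several scores on one day suits a score that is charted repeatedly.
- Protocol 7.3, exclusion 16c, uses a coma-score cut-off of 9, so that score takes values above 6.

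Pointing to the Outcome Score:
- Protocol 9.11 orders it at discharge.
- Its absence from the schedules is weak evidence. Discharge disposition is listed as an endpoint determination (Protocol 10.5, SAP 6.1.5) and has no schedule row either. Those two lists contain no Glasgow item at all.

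Both scores may be collected. The documents do not settle the question.

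**Size if the 6-point score is analysed.** Assumed codings: 1-6 or 0-5. Assumed scored patients per arm: 60, or 40 if 20 patients go to other facilities without a score and stay missing.

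Each home discharge set to 15 instead of the highest on-scale value:
- 60 scored: (15 − 6)/60 = 0.150; (15 − 5)/60 = 0.167
- 40 scored: (15 − 6)/40 = 0.225; (15 − 5)/40 = 0.250

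These are minimum shifts, because any lower on-scale value is further from 15.

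Each death set to 3 instead of the worst level. The distance from 3 to the two ends is 2 and 3 on 1-6, and 3 and 2 on 0-5, so it is 2 or 3 whichever end is worst:
- 60 scored: 2/60 = 0.033 to 3/60 = 0.050
- 40 scored: 2/40 = 0.050 to 3/40 = 0.075

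As an illustration, take the 25-40% mortality in Protocol 3.7.1 and suppose every death lacks a score. An arm of 60 would then have 15 to 24 imputed deaths, and its mean would move by 15 × 2/60 = 0.5 to 24 × 3/60 = 1.2 points. With equal arm sizes, only the difference between arms in the number imputed carries into the mean difference.

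**The case against.** The strongest reply is that the slip is obvious and harmless: the authors meant the coma score, for which 15 and 3 would be sensible values. On that reading no numerical error follows. But the endpoint is then misnamed throughout, its 6-point description is wrong, and a coma score would be reported as neurocognitive function. The text must change on either reading.

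The coma-score row also has another reason to exist. SAP 8.3 uses the Glasgow coma scale as the neurological component of SOFA. That weakens the inference from the row alone. SOFA is scored only on days 0, 3 and 7, however, and does not explain a measurement at discharge. The link to footnote J is an inference from a table whose markers may be misread, and the documents nowhere state that the coma score runs from 3 to 15. I therefore hold only moderate confidence that SAP 12.7.7 was written for it.

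SAP 12.7.7 also permits a median, and SAP 12.5 a rank test. With either, the distance from 6 to 15 carries no weight, so the home-discharge shifts apply only to a mean. The rank of an imputed death is still wrong, since 3 remains an inner level on the assumed codings.

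Finally, the sizes depend on a coding and a missing rate that the documents do not give. That is correct, and they should be read as illustration.

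**Conclusion.** The conflict is real, and nothing elsewhere in the documents resolves it: the rule in SAP 12.7.7 cannot be applied to a whole-step 6-point scale. Confidence is high on the conflict and low on the size of any effect.

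If the coma score is the instrument, the fault is in the name and the stated scale. If the Outcome Score is the instrument, the rule distorts its mean and misplaces imputed deaths, by the amounts shown and on the assumed codings. The effect is zero if no score is missing.

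Only one secondary endpoint is affected, and SAP 12.5 treats the secondary endpoints as supportive and exploratory. The primary analysis and the sample size are untouched. It should be fixed, but it does not threaten the trial's main conclusion.

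**What to change.** Before unblinding, state which instrument is analysed for the neurologic endpoint, even if both are collected. Then align the Protocol Synopsis, Protocol 6.2.1, 9.11, 10.5 and Appendix A with SAP 6.1.5, 7.2.1, 12.7.7 and Table 2.

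- **If it is the 6-point Outcome Score:** give its range, direction and death category in the SAP, delete the 15/3 rule, and place deaths in the death category. For other missing scores, either impute a value on the scale or leave them missing and report counts by arm.
- **If it is the coma score:** rename the endpoint, drop the 6-point description, and limit the conclusion under the neurocognitive objective to what that score measures.

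The cost is wording only, provided the chosen instrument was recorded at discharge; the case report forms are not in the documents, so this cannot be checked here. Changes to the protocol text go to the central IRB as an amendment (Protocol section 15). If the Outcome Score is chosen but was not captured, report it as not available rather than presenting the coma score under its name.

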12.7.8 Thromboembolic events

Thromboembolic events after study product administration will be listed by individual patient, with their allocated treatment and the occurring time of thromboembolic events, and will be summarized as patient counts and percentages by allocated group in modified ITT Population, and analyzed by Pearson's chi-square tests or Fisher exact tests, as appropriate.

12.7.9 Additional prognostic value of baseline fibrinogen

Baseline fibrinogen will be summarized by median with interquartile range. If it is skewed, log transformation will be applied to create normally distributed data. The predictive values of baseline fibrinogen for poor clinical outcomes, including hospital mortality by day 28 and day 60, will be assessed using the receiver operating characteristic (ROC) curve and the optimal cutoff values of fibrinogen will be determined using Youden's index.

To further evaluate the additional prognostic values of baseline fibrinogen on hospital mortality by day 28 and day 60, we will perform multivariate logistic Cox regression models which includes: baseline fibrinogen value, $\text{PaO}_2/\text{FiO}_2 < 150$ mmHg or ≥ 150 mmHg, study product assignment and any baseline parameters that suggests the evidence of randomization imbalance between two treatment groups. This model will also be performed in the subgroup of patients with COVID-19.

12.7.10 Biomarkers in Plasma and Urine

Plasma biomarkers, urine microalbumin and urine creatine, changes in levels of plasma SARS-CoV-2 viral antigen and antibody, as well as gene expression by treatment arm at multiple timepoints will be analyzed after the data is locked. The technician who independently perform the tests will be blinded to treatment. Concentration data will be identified as no sample (NS), not reportable (NR) and Below Limit of Quantification (BLQ) will be labelled as such in the listing.

To investigate the effects of hMSCs treatment on biomarker concentrations in plasma and urine, the concentrations of biomarker will be summarized and on the log-scale and/or on the log-transformed scale, by allocated treatments. Missing samples will be excluded from descriptive statistics. Values that are BLQ will be set at the limit of detection divided by two. Descriptive statistics of concentrations will be calculated only when at least 2/3 of the individuals have concentrations within the validated concentration range. We will then use the same modeling approach of a linear mixed-effects model.

To better understand the effects of hMSC treatment on clinical biomarkers in patients with COVID-19 disease, we will conduct the following additional analyses:

- Gene expression profiles will be compared by treatment arms, and stratified by: (1) SARS-CoV-2 infection (yes/no); (2) Dexamethasone or equivalent steroids therapy (yes/no); (3) Other immunomodulatory agents, then three separate linear mixed-effects models will be conducted by adjusting for SARS-CoV-2 infection, dexamethasone or steroids therapy, and other immunomodulatory agents.
- Changes in levels of protein biomarker measured in mini-bronchoalveolar lavage at day 2 from baseline will be compared by treatment arm, and stratified by: (1) SARS-CoV-2 infection (yes/no); (2) Dexamethasone or equivalent steroids therapy (yes/no); (3) Other immunomodulatory agents, then three separate linear mixed-effects models will be conducted by adjusting for SARS-CoV-2 infection, dexamethasone or steroids therapy, and other immunomodulatory agents.

